7. RESEARCH PROCEDURES

General Procedures. Subjects that meet the inclusion criteria will participate as outpatients at the University of Kentucky LHBP and Clinical Services Core (CSC). Subjects will be discharged at the end of each day, provided that they meet release criteria.

This experiment will require each subject to complete a total of one practice and nine experimental sessions over approximately two to three weeks. Experimental sessions will be conducted as outlined in the table below. We would like to note that the order of the experimental sessions (i.e., dose tested and craving manipulations) will be randomized across subjects. The practice session will familiarize subjects with the experimental routine and tasks, but no drug will be administered and subjects will receive instructions on each of the craving manipulation conditions (positive, negative, and look [neutral]).

Time	
0800	Arrival at LHBP. Drug and alcohol use restriction compliance verified. Transport to CSC.
0900	Baseline craving, subjective-effect and physiological measures completed.
1000	Subject samples intranasal dose available for that session. Subjective-effect and physiological measures completed at 15-minute intervals for 45 minutes. Commodity purchase tasks completed 15 minutes after sampling dose.
1045	Subject completes regulation of craving manipulation assigned for that session (positive, negative or look) and rates craving.
1050	Subject offered opportunity to work for dose on progressive-ratio schedule.
1100	Dose administered, if earned and physiological measures are within acceptable limits.
1115	Subjective-effects and physiological measures completed.
1130	Craving manipulation, craving measurement, progressive-ratio procedure and subjective-effects and physiological measures sequence completed. Repeats 4 more times at 45-minute intervals.
1530	Discharge from CSC. Return to LHBP for final sobriety testing, payment and release.
Note	Cocaine dose and craving manipulation will be presented in random order. A fully factorial design will be used so that all possible combinations are tested once each over nine sessions.

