Data Analysis. All data will be analyzed using SPSS (IBM Corporation, Armonk, NY). To test our primary hypothesis, self-reported craving scores and number of cocaine doses earned will be analyzed using two-factor repeated-measures General Linear Model (GLM) with data from the 30 subjects who complete the protocol. The α level will be set at $p \leq 0.05$. Data from subjects who do not complete will not be included in the analyses. Cocaine Dose (0, 40 and 80 mg) and Craving Manipulation (positive, negative and look) will be the factors of the ANOVA. A significant change in craving or self-administration will be inferred if the Interaction of Cocaine Dose and Craving Manipulation attains statistical significance. If the interaction attains statistical significance, the mean square error term will be used to conduct Tukey's HSD post-hoc test to make appropriate pair-wise comparisons. If baseline measures (e.g., craving) differ across conditions, they will be entered into the analysis as covariates. To test our secondary hypothesis, craving scores will be averaged for each of the nine conditions and compared with self-administration outcomes using Pearson correlations. Subjective-effect and physiological data following the sampling dose will be averaged across craving manipulation conditions because they will be collected prior to the craving manipulation and analyzed using cocaine dose and time as factors in a repeated-measures GLM. Exploratory analyses considering relevant biological variables (i.e., sex, age and race/ethnicity) will also be conducted.

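### The plan does not say how a baseline measured in each of nine sessions enters the repeated-measures GLM, and most ways of entering it leave the imbalance in place or cost power

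*Combined protocol and SAP*

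**What the plan says.** The Data Analysis paragraph of Section 7 (Research Procedures) names one primary model for both outcomes. Craving scores and number of doses earned "will be analyzed using two-factor repeated-measures General Linear Model (GLM) with data from the 30 subjects who complete the protocol". "Cocaine Dose (0, 40 and 80 mg) and Craving Manipulation (positive, negative and look) will be the factors of the ANOVA", and a change in either outcome is inferred only if their interaction is significant. The paragraph then adds: "If baseline measures (e.g., craving) differ across conditions, they will be entered into the analysis as covariates". It does not say in what form the baselines are entered, whether they are centred, or how a difference is to be judged.

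The session table in Section 7 has, at 0900 in every experimental session: "Baseline craving, subjective-effect and physiological measures completed". The note to that table says that "all possible combinations are tested once each over nine sessions". Each subject therefore has nine values of each baseline, one per dose-by-manipulation cell.

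**The concern.** The design is completely within-subject (Section 3), so a baseline that differs across conditions differs between a subject's own sessions. The usual repeated-measures GLM has one row per subject and nine outcome columns, and each covariate takes one value per subject. Such a value cannot explain why one session of a subject differs from another.

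An analyst following the covariate sentence would have to choose between a subject mean and nine separate columns, and then choose a centring. These choices give different tests of the interaction, which is the only gate to a positive conclusion and to the Tukey comparisons. A poor choice could lose a real effect, produce a false one, or leave the result unchanged while it is reported as baseline-adjusted. The sentence takes effect exactly when an imbalance has been seen.

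**Working it through.** The documents give no SD, effect size or power figure, so there is nothing to reproduce. The algebra needs no assumed values; the sizes do.

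**Inputs from Section 7.** n = 30 completers; 3 × 3 = 9 cells, each tested once; interaction with 4 df; α = 0.05; craving on a 0–10 scale.

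**Assumed inputs.** Both sets use baseline mean 5, between-subject SD 2 and residual SD 1. Under the negative instruction, craving falls at 40 and 80 mg only.
- Set A: within-subject (session-to-session) SD of baseline 1.5, slope of outcome on baseline 0.6, effect 1.3.
- Set B: within-subject SD 1.0, slope 0.3, effect 1.0.

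**Algebra.** Let Y = subject effect + β·X + τ + error for each session, with X that session's baseline. For an interaction contrast w, whose weights sum to zero, the subject's score is w′Y = w′τ + β·w′X + error. The GLM regresses this score on the covariates and tests whether the intercept is zero.

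- *Subject mean, centred.* The intercept is the mean contrast, w′τ + β·w′X̄. All of the imbalance w′X̄ remains.
- *Subject mean, raw.* The test moves to baseline = 0. The intercept's variance is multiplied by about 1 + n·5²/[(n − 1)·Var(subject mean)]. In Set A, Var = 4 + 1.5²/9 = 4.25, giving 1 + 750/123.25 = 7.1.
- *Nine raw columns.* The imbalance is removed, but the test is again at all baselines = 0, far from the data.
- *Nine columns, each centred on its own mean.* The intercept is still the unadjusted mean contrast. Its true variance is proportional to β²·SD² + 1 (1.81 in Set A, 1.09 in Set B), but the error term estimates 1.
- *Nine columns centred on the grand mean.* The test is at equal baselines in all cells, so the adjustment is valid. Error df per contrast fall from 29 to 20.
- *Same-session covariate in long format.* The imbalance is removed for one error df.

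**Closed-form checks.** The interaction sum of squares is effect² × 4/9: 0.751 (A) and 0.444 (B).
- No covariate: λ = 30 × 0.751/1.81 = 12.4, power 80% (A); λ = 30 × 0.444/1.09 = 12.2, power 79% (B).
- Subject mean raw, A: λ = 12.4/7.1 = 1.76, power 15%.
- Same-session covariate: λ = 30 × 0.751 = 22.5, power 98% (A); λ = 13.3, power 84% (B).
- Own-mean-centred, false positives: the 5% critical value of F(4, 80) is 2.49. P(F > 2.49/1.81) = 25% (A); P(F > 2.49/1.09) = 7% (B).

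**Simulation, covariate entered in every trial.**

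| Entry | Imbalance left | Power A | Power B | False positives |
|---|---|---|---|---|
| None | all | about 81% | about 80% | about 5% |
| Subject mean, centred | all | no gain | no gain | about 5% |
| Subject mean, raw | all | 15% | 15% | about 5% |
| Nine raw | none | 18% | 12% | about 5% |
| Nine, own-mean-centred | all | not a valid test | not a valid test | 25% (A), 7% (B) |
| Nine, grand-mean-centred | none | 89% | 66% | about 5% |
| Same-session covariate | none | 98% | 84% | about 5% |

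The false-positive column averages over all trials. With a centred subject mean the rate is higher in trials where an imbalance has been seen. Further simulations (residual SD 1.5, slopes 0.3 to 0.9) put it at 7% to 24% when the baseline interaction has p < 0.05.

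**Allowing for the conditional rule.** Suppose the rule triggers when any of the three effects on baseline craving (dose, manipulation, interaction) has p < 0.05. The chance is about 1 − 0.95³ = 14%. Power in Set A with raw subject-mean entry is then about 0.857 × 80% + 0.143 × 15% = 71%. Simulated false positives with own-mean-centred columns are about 8.5% in Set A and 5% in Set B.

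**The case against.** A reader might infer that the named model cannot make the adjustment at all, that any entry leaves the imbalance in place, and that the trial's power or error rate is wrecked. The documents do not support that.

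- Nine columns centred on the grand mean adjust validly inside the one-row-per-subject GLM. In Set A they gain power over no covariate (89% against 81%); in Set B they lose it (66% against 80%). Nine raw columns also remove the imbalance; their defect is power.
- The plan names SPSS and a repeated-measures GLM but no data layout. A long-format linear model with subject effects could fairly be given the same name.
- Session order is random ("Cocaine dose and craving manipulation will be presented in random order"), so imbalance should arise only by chance and the covariate is entered only in some trials. The 15% and 25% figures do not describe the trial as a whole.
- The model without covariates is sound, and this is a pilot study.

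All of this stands and limits the size of the point. It does not reduce it to a missing detail. The entries an analyst would most readily try are the subject mean and the nine columns as recorded. The first adjusts nothing and the second loses most of the power, in just those trials where adjustment was wanted. The plan specifies neither of the two entries that work well.

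**Conclusion.** The point holds as a gap in specification with real consequences. That a subject-mean covariate leaves the whole imbalance in place is algebra and rests on no assumed figure. The sizes rest on the assumed SDs, slope, baseline mean and effect. Raw-entry power depends strongly on the baseline mean: in a further simulation (slope 0.6, residual SD 1.5) it was about 32%, 15% and 10% at baseline means of 2, 4 and 6.

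When the covariate is entered, raw entry takes power from about 80% to between 12% and 18%, and own-mean-centred columns give about 7% to 25% false positives. Over all trials, at a 14% trigger rate, the cost is about nine or ten points of power with raw entry, or false positives up to about 8.5%. Testing more baselines would trigger the rule more often. Only a continuous, craving-like outcome was simulated; doses earned, a count from 0 to 5, was not. This should be changed, but it does not invalidate the trial.

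**What to change.** Amend the covariate sentence in Section 7, Data Analysis. State that craving and doses earned are analysed in long format, one row per subject-session, with subject effects, Dose, Manipulation and Dose × Manipulation. Add the same session's own 0900 baseline craving as a session-varying covariate, included whether or not baselines differ. Base the pairwise comparisons on that model's adjusted means and error, so that they test the same adjusted quantities as the interaction.

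The cost is a few lines of text, a long-format dataset, slightly more analysis work and one error df. The software is the same, and the 0900 baselines are already collected.

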Subjects will be encouraged to abstain from illicit drugs for the duration of the study and from alcohol for the 12 hours prior to, and following, each experimental session. They must also agree to abstain from solid food and caffeine for 4 hours before each experimental session. Subjects will arrive at the LHBP at approximately 0800 hours. Upon arrival at the LHBP, a breathalyzer and a field sobriety test will be conducted, a urine sample collected, and pre-session paperwork completed. A breathalyzer positive for alcohol or a urine sample positive for recent use of amphetamines, benzodiazepines, barbiturates, or opioids will preclude the subject from participation in the session. If a subject tests positive for recent use of cocaine or marijuana (THC), [name] or [name] must be notified. Subjects will only be allowed to participate in a session with a marijuana or cocaine positive urine if they pass the sobriety testing and baseline cardiovascular measures are within acceptable limits (i.e., heart rate < 90 bpm, if systolic pressure < 140, or diastolic pressure < 90). Moreover, intranasal cocaine doses may not be administered until two hours following all subjects' arrival, regardless of the outcome of their urinalysis. Subjects will then be provided with a standard, fat- and caffeine-free breakfast. Prior to beginning each experimental session, subjects that report smoking tobacco cigarettes will be allowed to smoke one cigarette.

At 0830, subjects will be transported to the CSC. Physiological measures will be recorded at 15-minute intervals upon arrival at the CSC. At 1000, subjects will sample the dose of intranasal cocaine available that day (0, 40 or 80 mg). After sampling the drug, subjects will complete the subject-rated measures. Subjects will then make 5 choices to self-administer the sampling dose after completing the craving manipulation. Choices will be separated by 45 minutes. Drug administration will be withheld if heart rate > 90 bpm, if systolic pressure > 140 or

diastolic pressure > 90. Subjects will be excluded from further research participation if at any time during an experimental session heart rate increases above 130 bpm, diastolic pressure increases above 110 mmHg or systolic pressure above 180 mmHg.

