During the actual manipulation in experimental sessions, subjects will be presented 30 trials depicting cocaine images. Each trial will begin with an instruction presentation (i.e., positive, negative, look) followed by 6-second image presentation. The instruction presentation will remain constant within each experimental session. Images will be presented in random order from a bank of 300 images to minimize habituation. After each image offset, subjects will rate craving for cocaine using a 0-10 visual analog scale (0 = Not at All; 10 = Very Much) (Lopez et al., 2015). Craving, averaged across all trials in a session, will be the primary outcome. The manipulation will be repeated prior to each self-administration opportunity.

Progressive-Ratio Procedure. Following a 30-image trial, subjects will be offered the opportunity to earn the sampled cocaine dose on the Progressive-Ratio Procedure. We have a long history of using this procedure to assess the reinforcing effects of stimulant drugs ([name], 2008), including cocaine ([name] et al., 2010a; 2012a). It yields orderly, dose-related self-administration outcomes. Subjects will have a total of five opportunities to earn the dose they sampled at the outset of the session in order to provide multiple replication trials to determine the impact of the craving manipulation on drug self-administration (Ferster and Skinner, 1957; Spiga and Roache, 1997). The initial response requirement for a dose will be 400 mouse clicks. Response requirements will increase by 200 for each subsequent dose. For example, if a subject chooses cocaine at the first trial, earning that dose would require 400 responses. At the second opportunity, if he/she chooses to earn cocaine again, earning that dose would require 600 responses. If he or she elects not to earn cocaine at any given opportunity, the response requirement would not increase for the next opportunity. If a subject were to choose cocaine across all opportunities, the response requirements would be 400, 600, 800, 1000 and 1200 responses. The primary outcome is the number of cocaine doses earned.

Subjective-Effects and Physiological Measures. A subjective-effects questionnaire and physiological measures will also be used to assess cocaine effects and monitor safety.

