Potential subjects will provide information regarding their drug use history and undergo an extensive physical and psychiatric health screening to determine their eligibility and safety of their participation. Any potential subject with a history of clinically significant physical disease, current physical disease (e.g., impaired cardiovascular functioning, histories of seizure, head trauma or CNS tumors), or current or past histories of psychiatric disorder that in the opinion of the study physician would interfere with study participation, other than substance use disorder, will be excluded from research participation. Females must be using an effective form of birth control in

order to participate and must not be pregnant. Methods for monitoring adverse events (AEs) will include observations by the medical and research staff, spontaneous report by the subjects and, regular measurement of cardiovascular function. Subjects will not receive study drug if they have any signs or symptoms that may contraindicate its administration (e.g., HR and BP outside of predetermined range, development of serious side effects).

All AEs occurring during the course of the study will be collected, documented and reported to the PI. The occurrence of AEs will be assessed for the duration of participation. Each week a study investigator will review the AE forms from the previous week for events that were reported as new or continuing. The study investigators will follow all AEs to the point of a satisfactory resolution. Subjects may be withdrawn from the study if the medically responsible investigator determines it is the best decision in order to protect the safety of the subject. All AEs will be assessed to determine if they meet criteria for a serious adverse event (SAE).

Serious Adverse Events, as defined by the FDA, will be systematically evaluated for the duration of participation. Any SAE, whether or not related to the study drug, will be reported to the IRB, CSC, and the FDA. The initial SAE report will be followed by submission of a completed SAE report to all three institutions.

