In the event that a subject either withdraws from the study or the investigator decides to discontinue a subject due to an SAE, the subject will have appropriate follow-up medical monitoring. Monitoring will continue until the problem requiring hospitalization has resolved or stabilized with no further change expected, is clearly unrelated to the study drugs, or results in death. Outcome of SAEs will be periodically reported to IRB, CSC, and the FDA. A summary of the SAEs that occurred during the previous year will be included in the annual progress report to the IRB, CSC, and FDA.

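### Dropping every finished session of non-completers biases post-sampling cardiovascular effects low by an unknown, probably small amount and discards usable data; the primary contrast is barely affected.

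*Combined protocol and SAP*

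**What the plan says.** **Analysis set.** Section 7, Data Analysis, plans repeated-measures GLMs on the 30 subjects who complete, and adds: "Data from subjects who do not complete will not be included in the analyses". Completion means nine experimental sessions, one for each pairing of three doses with three instructions. Section 4 sets the target as thirty completers.

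**Routes out.**
- Section 7, General Procedures: "Subjects will be excluded from further research participation if at any time during an experimental session heart rate increases above 130 bpm". Limits for diastolic (110 mmHg) and systolic (180 mmHg) pressure follow in the same sentence.
- Section 17, Safety Monitoring Plan: "Subjects may be withdrawn from the study if the medically responsible investigator determines it is the best decision". The plan also provides follow-up when "a subject either withdraws from the study or the investigator decides to discontinue a subject due to an SAE".
- Section 4 stops participation on pregnancy, and section 12 on an expressed wish for treatment.

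**What is analysed.** The session schedule in section 7 has "Subjective-effect and physiological measures completed at 15-minute intervals for 45 minutes" after the sampling dose. For the analysis, "Subjective-effect and physiological data following the sampling dose will be averaged across craving manipulation conditions", with dose and time as factors. Later in the session, "Subjects will have a total of five opportunities to earn the dose they sampled at the outset of the session".

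**What is not restricted.** Section 17 says: "All AEs occurring during the course of the study will be collected, documented and reported to the PI". Adverse-event collection is therefore not limited to completers.

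The plan gives no removal rate, no method for incomplete data and no sensitivity analysis.

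**The concern.** Heart rate and blood pressure help to decide who stays, and they are also outcomes. The protocol calls them sensitive to stimulants (section 7, Physiological Measures) and says that side effects, which include raised heart rate and blood pressure, depend on dose (section 9). Subjects with the largest responses are the most likely to be removed, and all their earlier data then go with them. Recruiting replacements restores the count of 30 but not the mix of subjects who started.

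Two things are at stake. The 80 mg versus 0 mg cardiovascular effect would describe subjects selected for tolerating cocaine. Finished sessions, obtained by giving cocaine to volunteers, would also be lost to the within-subject comparisons.

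**Working it through.** The plan has no figure to reproduce: the 30 completers come without an effect size, SD, power or dropout rate. Removal rates and response distributions below are assumptions.

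**1. Upper bound on the cardiovascular bias.** Suppose the post-sampling rise is normal between subjects and the fraction q with the largest rises is removed. The completer mean then falls by φ(z)/(1−q) SD, where z is the (1−q) normal quantile. If the removal trigger correlates r with the rise, multiply by r.

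| q | z | φ(z) | shift, r = 1 | shift, r = 0.5 |
|---|---|---|---|---|
| 1% | 2.326 | 0.0267 | 0.03 | 0.01 |
| 5% | 1.645 | 0.1031 | 0.11 | 0.05 |
| 10% | 1.282 | 0.1755 | 0.20 | 0.10 |
| 20% | 0.842 | 0.2800 | 0.35 | 0.17 |

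The correlation should be below 1. A session holds 1 + 5 = 6 possible doses, and only the sampling dose precedes the analysed 45 minutes. Removal can follow any of the later five.

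**2. The same bias in bpm.** A simulation of 60,000 subjects assumed a baseline of 72 (SD 8), mean rises of 0, 8 and 15 bpm at 0, 40 and 80 mg, skewed reactivity, and a peak that grows with each earned dose. With 8–12% removed, the true 80-versus-0 mg effect of about 15.0 bpm became 13.6, 13.2 and 13.0 bpm in completers, for correlations of −0.5, 0 and 0.4 between reactivity and the tendency to earn doses. That is about 9–14% low. With about 1% removed it became 14.6 (correlation 0), or 2.5% low.

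**3. Doses earned.** In the same simulation the 80 mg mean moved by +0.02, −0.05 and −0.12 doses for those three correlations. A second model removed 10% on reactivity alone, without accumulation from earned doses. It moved an 80 mg/look mean of 3.48 to 3.57, 3.53, 3.48 and 3.43 for correlations of −0.5, −0.3, 0 and +0.3. The sign depends on a correlation that the documents do not give. Craving was not simulated.

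**4. Primary contrast.** The positive-minus-negative difference at 80 mg less that at 0 mg was 0.46–0.47 in truth and 0.46–0.48 in completers. Another model removed subjects at 15% (80 mg) or 5% (40 mg) per session in which at least four doses were earned. There the negative-minus-look contrast at 80 mg was −0.89 in truth and −0.91 in completers. Neither model linked leaving to the response to instruction.

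**5. Sessions lost.** Starters needed are 30/(1−q), and the analysed set is 30 × 9 = 270 sessions. The simulation gave roughly 2.4–3.0 finished sessions before removal.

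| q | starters | removed | sessions lost, typical | maximum (8 each) |
|---|---|---|---|---|
| 5% | 32 | 2 | 5–6 | 16 |
| 10% | 34 | 4 | 10–12 | 32 |
| 20% | 38 | 8 | 20–24 | 64 |

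**6. What an all-sessions model recovers.** With r = 1, a mixed model that keeps the removal-session readings is low by 0.01, 0.04, 0.07 and 0.13 SD at the four rates. Dropping those readings gives 0.02, 0.08, 0.15 and 0.28.

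For the interaction test with no dropout:

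| model | power | type I error |
|---|---|---|
| planned GLM | 0.72 | 0.051 |
| mixed model set out under the fix | 0.73 | 0.052 |
| random intercept only | 0.65 | 0.031 |

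Under the heavy 15%/5% removal of step 4, power is 0.785 for that mixed model against 0.738 for the completer GLM.

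**The case against.** The strongest reply is that little is at risk. Section 7 withholds doses at limits well below those for removal and reports earlier use of these unit doses without incident. Section 9 calls side effects unlikely. At 1% removal the bias is at most 0.03 SD. The planned inference rests on a within-subject interaction that hardly moves, and recruiting to 30 completers keeps the planned size and balance. A mixed model only reduces the bias. All of this stands, and it limits the gain. It does not justify the rule, because finished sessions are lost whenever anyone leaves and the alternative costs almost nothing if nobody does.

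A reader might infer more than the documents support:
- *Mean doses earned or craving at active doses are understated.* Nothing links cardiovascular response to either. Earned doses could accumulate and push high earners out, but strong responders might instead choose fewer doses.
- *The primary test is invalid.* That would require leaving to depend on the response to instruction, which nothing in the documents indicates.
- *Heart rate and blood pressure alone decide who leaves.* They are one of several routes.
- *Safety reporting omits non-completers, or their numbers will stay hidden.* Adverse events are collected for everyone, and silence on a disposition table does not show that none will be produced.

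**Conclusion.** The concern holds in a limited form. Relative to those who started, post-sampling cardiovascular effects in completers are biased low whenever removals on those variables occur. The size depends on an unstated rate. It is at most 0.03 to 0.35 SD for 1% to 20% removal if the response is normal, and less if the trigger is only partly correlated with the post-sampling rise. The direction for doses earned and craving is open. For the dose-by-manipulation contrast the cost is precision, which is small if few leave.

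This is a minor point in a pilot study. The gain lies in secondary physiological results and retained data, not in the validity of the primary test.

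**What to change.** Replace the completers-only sentence in section 7, Data Analysis, with a linear mixed model (SPSS MIXED) on all available sessions of every subject with at least one completed experimental session.

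- **Craving and doses earned:** fixed dose, manipulation and interaction, with random subject, subject-by-dose and subject-by-manipulation effects. The interaction test then matches the planned GLM when nobody leaves. Do not use a random intercept alone.
- **Post-sampling subjective and physiological data:** dose and time with corresponding random effects. Keep all readings within the 45-minute window, including those from the session in which removal occurred.
- **A doses-earned count cut short by removal:** treat as missing.
- **Sensitivity analysis:** the planned GLM on the 30 completers.
- **Reporting:** tabulate non-completion by reason and by last dose and instruction received.

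The cost is slightly more analysis work, random effects that must be written out, and reliance on missing-at-random. A count set to missing because of removal does not fully meet that assumption, so the bias is reduced but not removed. The clinical limits and the recruitment target are unchanged.
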